1.1 Synopsis

Protocol Title: A Phase 4, Multi-center Open-label Feasibility Study to Evaluate Outpatient Blinatumomab Administration in Adult Subjects with Minimal Residual Disease (MRD) of B-precursor Acute Lymphoblastic Leukemia (ALL) in Complete Hematologic Remission

Short Protocol Title: Phase 4 Feasibility Study to Evaluate Outpatient Blinatumomab in Subjects with MRD of B-precursor ALL

Study Phase: Phase 4

Indication: Adult subjects with MRD of B-precursor ALL

Rationale

This **study aims** to determine the safety and feasibility of complete outpatient blinatumomab administration for subjects with **minimal/measurable residual disease** (MRD) of B-precursor ALL. Blinatumomab administration has been demonstrated to be efficacious in this population for converting subjects to MRD negative status. However, the mechanism of action of T cell activation and cytokine production can result in potentially severe toxicity, specifically Cytokine Release Syndrome (CRS) and/or neurotoxicity (NT). The incidence of these potentially severe side effects has been shown to be low. In the BLAST study, 3% and 13% of subjects had severe CRS and NT respectively (Gökbuget et al, 2018).

The objective of this study is to determine the safety and feasibility of complete outpatient blinatumomab administration for subjects with MRD of B-precursor ALL. The study will use mobile electronic devices (tablet) to electronically communicate with the healthcare provider (HCP) or designee. The designee will be any person selected by the principal investigator who has experience with and is trained on the management of patients with serious medical conditions (eg, acute leukemia), and who has received training on the protocol, the Current Health (CH) devices, and Current Wearable Health Monitoring System (CWHMS) outpatient monitoring. Examples of designees include sub-investigators, study nurses, or physician extenders (eg, nurse practitioners, physician assistants, etc). A designee can also be trained medical personnel provided by CH who is trained on the protocol, the CH devices, and CWHMS outpatient monitoring. If the Principal investigator selects a designee provided by CH, CH will document that the designee is trained on the protocol and devices, is qualified to triage health and technical alarms and

Date: 21 April 2022 Page 9 of 108

meets the above criteria. The use of the term HCP, henceforth, will refer to the HCP or designee. A Wi-Fi and cellular enabled platform will be used for the transfer of data and communication between subject and HCP to detect clinically important changes. The data provided to the HCP will enable him/her to identify subjects at risk of developing grade 3 or 4 CRS, NT, or other serious adverse events (SAEs) requiring hospitalization during the mandatory device monitoring period (MDMP; see Section 3). The HCP can then direct such subjects to the appropriate medical facility for hospitalization if needed.

Objective(s)/Endpoint(s)

Objectives	Endpoints						
Primary							
 To determine the safety of outpatient blinatumomab administration, during the MDMP (defined as the first 3 days of cycle 1 and first 2 days of cycle 2 of outpatient blinatumomab infusion) 	Incidence of grade 3 and/or 4 CRS, NT or any adverse event (AE) requiring hospitalization (SAE) during MDMP.						
Secondary							
To determine the time from first detection of grade 3 or 4 vital sign, or significant clinical change to therapeutic intervention (any measurable action taken by or performed on the subject due to onset of the clinical parameters described above) during the MDMP	Time (in minutes) from first onset of fever, hypotension, hypoxia, other grade 3 or 4 vital sign including seizure or neurological change (grade 3-limiting self-care activities of daily living [ADL]) to therapeutic interventiona						
 Evaluate the safety and tolerability of blinatumomab administered exclusively as an outpatient 	Overall incidence and severity of treatment-emergent adverse events (TEAE) and adverse events of interest in particular CRS and NT.						
 Evaluate the impact of complete outpatient blinatumomab treatment on patient reported outcome (PRO), global health status (GHS), and quality of life (QoL). 	European Organisation for Research and Treatment of Cancer (EORTC) validated electronic version of QLQ-C30.						
Estimate healthcare resource utilization associated with treatment-related AEs	 TEAEs that resulted in hospitalizations TEAEs that resulted in surgeries. TEAEs that resulted in the use of concomitant medications TEAEs that resulted in the use of device/procedure intervention. 						

Date: 21 April 2022 Page 10 of 108

ADL = activities of daily living; AE = adverse event; CG = caregiver; CRS = cytokine release syndrome; EMS = Emergency Medical Service; EORTC = European Organisation for Research and Treatment of Cancer; GHS = global health status; HCP = Health Care Provider; IV = intravenous; MDMP = mandatory device monitoring period; NT = neurotoxicity; PO = by mouth; PRO = patient reported outcomes; QLQ-30 = Quality of Life of Cancer Patients; QoL = quality of life; SAE = serious adverse event; TEAE = treatment-emergent adverse event.

^a Therapeutic intervention is any measurable action taken by the subject or performed on the subject as a result of the onset of the clinical parameters described. Such actions may include: Advice from HCP to immediately call EMS or dial 911, discontinuation of the blinatumomab infusion, subject taking an oral medication, subject receiving a medication or intervention by any emergency or hospital medical services, intervention such as administering any medication (IV or PO or PR) or IV fluids or oxygen etc. Time to therapeutic intervention (TTI) is the measured time between the delivery of the device alert or unscheduled contact with HCP by subject/CG to report a change to the time of initiation of the therapeutic intervention as defined.

Background and Rationale

This study **aims** to determine the safety and feasibility of complete outpatient blinatumomab administration. Blinatumomab is a novel bispecific T-cell engaging (BiTE) single-chain antibody construct that links CD3+ T lymphocytes with CD19+ B cells. This may result in a significant degree of T cell-mediated immune activation in subjects, which has correlated with efficacy but also with notable toxicity. The result is a heightened T-cell activation and release of pro inflammatory cytokines and the clinical manifestation of CRS. Along with CRS, another potentially severe toxicity observed is NT. Subjects may show signs of encephalopathy with varying degrees of severity and may experience delirium, aphasia, lethargy, difficulty concentrating, agitation, tremor, seizures, and, rarely, cerebral edema.

Minimal/measurable residual disease is defined as the presence of leukemic cells not detectable by microscopy (< 5%) measured either by polymerase chain reaction (PCR) or flow cytometry. After achieving hematologic remission, the presence of MRD portends a poor prognosis for patients. In the Amgen trial MT103-203 (BLAST), 78% of subjects with MRD of B-precursor ALL achieved a complete MRD response to blinatumomab therapy. In this trial, 4 subjects (3%) had CRS (Common Terminology Criteria for Adverse Events [CTCAE] v4 grade 1, n = 2; grade 3, n = 2), all during cycle 1. Twelve (10%) and 3 subjects (3%) had grade 3 and 4 NT, respectively. Moreover, subjects with relapsed/refractory B-precursor ALL treated with blinatumomab in the Amgen trial 00103311 (TOWER) similarly had a low incidence of CRS and NT. In the 00103311 study the incidence of grade \geq 3 CRS and NT were 4.9% and 9.4%, respectively with 1% and 4.9% of subjects having their treatment discontinued due to CRS and NT, respectively (Kantarjian et al, 2017).

The current recommendation for blinatumomab treatment for subjects with MRD of B-precursor ALL is continuous intravenous infusion (CiVI) for 28 days, with the first

Date: 21 April 2022 Page 11 of 108

3 days in cycle 1 and the first 2 days in cycle 2 administered in the inpatient setting. This recommendation for hospitalization is primarily for safety concerns of CRS, NT, or other severe **adverse events (AEs)**.

This study **aims** to determine the safety and feasibility of complete outpatient blinatumomab administration for subjects with MRD of B-precursor ALL. The study will use the CWHMS that is comprised of **CH** wearable **device** worn on the **subject's** upper arm, **an** axillary temperature patch, a blood pressure cuff, a Wifi hub, tablet, **a** mobile phone **provisioned to the HCP**, and a platform will also be used to monitor subjects' vital signs while they are at home.

This study will include the following:

- Remote monitoring using CWHMS to measure vital signs and mobile electronic devices (tablet) to electronically communicate these vital signs with the HCP.
- The use of a Wi-Fi and cellular enabled platform for the transfer of data and communication between subject and HCP, to identify subjects at risk of developing grade 3 or 4 CRS, NT or other SAEs requiring hospitalization during the MDMP.
 This subject group may require immediate escalation of care and/or hospitalization once the digital monitoring system identifies changes.

Design

During screening, subjects and caregivers will be trained on the CWHMS and assessed for compliance (Table 1-1, panel 1). **Once enrolled,** subjects will receive 2 **complete** cycles of blinatumomab in the outpatient setting in accordance with the monitoring and intervention guidelines (Table 1-1., panels 2 and 3).

After the end of cycle 2 clinical assessment visit, some subjects may continue to receive 2 additional (optional) cycles of **outpatient** blinatumomab. There will be no CWHMS outpatient monitoring during the optional cycles 3 and 4. For the purpose of this study, the MDMP is defined as the first 3 days of cycle 1 (72 hours) and the first 2 days of cycle 2 (48 hours) of blinatumomab infusion for subjects with MRD of B-precursor ALL.

The end of study visit will occur 30 days (+ 3 days) after the last dose of blinatumomab is administered (Figure 1-1).

During the MDMP, the CWHMS will measure vital signs. These vital signs include **pulse** rate, **respiratory rate**, oxygen saturation, **and axillary temperature**. The CWHMS will measure respiratory rate intermittently (sampling every 30 seconds). The subjects will

Date: 21 April 2022 Page 12 of 108

Product: Blinatumomab
Protocol Number: 20190014

take intermittent blood pressure (BP) measurements (using a subject-usable BP device) every 3 hours during the MDMP. The schedule for BP measurements may be extended by HCP (up to but not exceeding every 6 hours) after the first 24 hours of MDMP. The BP device will be provided and will directly transmit the BP reading via the monitoring platform to the **CH Patients Application on the study provisioned mobile phone**.

Threshold vital sign values will be established, and an immediate alert will be generated and transmitted to the **monitoring platform** once the preset threshold values are surpassed and sustained for at least 10 minutes (Table 1-1). **Except for blood pressure**, an alert will be triggered within 1 minute upon being received.

In addition, subject and caregiver will be trained on the usual side effects of blinatumomab infusion (fever, erythematous skin rash, chills, confusion, headache, tremor, myalgia, lethargy, somnolence, seizure), and have direct (phone and video) contact with HCP or emergency services if any expected or unexpected side effects occur. The caregiver is expected to be a spouse or close relative such as a child but can be any adult (≥ 18 years) willing and able to participate in the subject's care. The caregiver will remain in the home with the subject for the entire MDMP. The caregiver will be trained to use and have access to the tablet for communication with the HCP, if necessary.

The HCP and the staff will also be trained on the infusion, usual side effects and response algorithm (Table 1-1). The HCP will be **trained** in the treatment of patients with ALL and the use of blinatumomab. The HCP will carry the **study provisioned mobile phone** at all times during the MDMP. The **study provisioned mobile phone** will have cellular connection to the subject's tablet and the CWHMS and will receive vital signs refreshed every 30 seconds for the entire MDMP. Blood pressure will be performed manually by the subject (or caregiver) every 3 hours and the result electronically delivered to the **study provisioned mobile phone**. In addition to the continuous feed of vital signs, an audible alarm will sound every time the vital signs exceed the preset threshold and is consistent for at least 10 minutes. In addition, an audible alarm will sound if there is no data transfer for 15 minutes.

It is not intended that the CWHMS will allow the HCP to identify patients experiencing neurotoxicity. The CWHMS is intended to provide remote monitoring of vital signs. Knowing a subject's vital signs will give the HCP an overall picture of the subject's disposition. In addition to vital signs monitoring, the CWHMS includes the functionality for video calling between the **HCP** and the subject. This allows the HCP to visually

Date: 21 April 2022 Page 13 of 108

assess the patient for early symptoms of mild neurotoxicity such as kinetic tremor (assessed by finger-nose test), ataxia, appearance of disorientation to time or place, impaired attention or short-term memory with preserved alertness, impaired naming, paraphasic errors, or verbal perseveration. The HCP will also test the patient's ability to name objects, follow simple commands, and communicate their needs. The HCP will evaluate expressive aphasia by evaluating the subjects' ability to communicate spontaneously (for example HCP may instruct subject to "look directly on the video screen and tell me how you are feeling today") or in naming a common household object provided by caregiver. Healthcare professional will evaluate apraxia by the subject's ability to write a standard sentence (for example "Today is Tuesday January 1, 2001"). HCP will test receptive aphasia by the subject's ability to follow a simple command (for example "Lift your right hand and touch your nose").

In addition, the caregiver will be present with the patient for the entire MDMP and will be able to communicate and participate with the HCP during the video call assessment. The HCP will use this video call assessment to determine if the patient's symptoms (as defined for neurotoxicity in Section 11.8) necessitate immediate transfer to hospital. The HCP will schedule video calls with the patients a minimum of every 12 hours (eg, 8 am and 8 pm) daily during the MDMP. The frequency may be increased if there are any concerns by the HCP.

The monitoring system also provides the functionality for the patient or caregiver to activate an "I don't feel well" button on the device tablet in the event of the subject experiencing any neurological symptoms. Activating the button immediately generates an alarm and notifies the HCP and allows for an immediate video call assessment to be initiated. Healthcare professional will advise transfer of subject to an inpatient facility if any of the neurological symptoms are greater than mild in severity. In addition, as part of screening, patients and caregivers will be trained to activate the "I don't feel well" button for any moderate symptoms of speech disorders, disturbances in consciousness, deterioration of hand writing, confusion or disorientation.

Subjects will be trained to resend the "I don't feel well" signal if no response from the HCP is received in 5 minutes. If there is still no response after another 5 minutes, 10 minutes total from the initial alarm, then the subject or caregiver is to call Emergency Medical Service (EMS) or dial 911 immediately. Likewise, if the HCP responds to any alarm generated from the subject and the subject or caregiver does not answer within 10 minutes, then the HCP will make 1 attempt to call the subject's personal phone. If the

Date: 21 April 2022 Page 14 of 108

subject or caregiver is still not reachable, the HCP will have EMS dispatched to the subject's location immediately.

The **study provisioned mobile phone** is configured so that a loud audible alarm is made and repeated every 5 minutes until the HCP responds or if no data is transferred for 15 minutes.

The HCP will then use the compendium of vital sign's absolute value and/or deviation from baseline (provided by the CWHMS) and the subject's clinical status (provided by direct subject/caregiver telephone and video contact), to make decisions on urgency of response, appropriate intervention and subject disposition.

During MDMP, any device malfunction that results in lack of data transmission (eg, from the CH wearable device, axillary temperature patch) for 15 minutes will generate an alarm to the HCP. The HCP will contact the patient immediately via the video calling functionality to assess the patient's safety, clinical status, and any specific circumstances associated with the device malfunction (eg, device inadvertently dislodged, low battery charge, intermittent loss of signal transmission etc). If the HCP has any concern of patient safety, HCP will advise the patient to immediately go to the hospital.

Patients are provided with a full set of replacement devices to be used in case of a malfunction. In addition, a manual oral thermometer will be provided to the patients, as needed or directed by the HCP. In the case of a device malfunction and the HCP decides that the patient is safe via the video conference, the HCP will direct the patient to switch to the replacement device(s) immediately. In addition, HCP may contact Current Health's 24/7 help hotline for device support and troubleshooting for assistance. It is recommended that the HCP remain in contact with the subject until device malfunction is resolved. If these interventions by HCP fail to resolve the device malfunction, then HCP will advise the patient to proceed immediately to the hospital. Only United States (US) Food and Drug Administration (FDA) cleared vital sign monitoring devices and platform will be used. During the MDMP, subjects will be required to live no more than 1-hour transportation by car from an advanced medical care facility. An advanced medical care facility is 1 with staff trained to manage acutely ill patients such as those who may be developing CRS. Subjects will be allowed to stay at a hotel or other outpatient hospital housing facilities to fulfil the 1-hour transportation requirement. Subjects will be trained to call emergency medical services for any concerns or for any delay in communication with the HCP.

Date: 21 April 2022 Page 15 of 108

Subjects will be provided with a dedicated in-house Wi-Fi device (home hub) for the sole purpose of uninterrupted transmission of vital signs and for communication including video contact with the HCP. Subjects and caregivers should contact their HCP for support with any technical issues relating to the CWHMS. The HCP will have access to a 24/7 help hotline for any technical issues relating to the CWHMS.

Subjects will not have access to this hotline, they will need to contact HCP who can contact the hotline.

Sites would be given the option to utilize nursing triaging services provisioned by CH to act as their designee to acknowledge and respond to health and technical alarms during a subject's MDMP. Details are discussed in Section 8.2.2.1.

The overall study design is described by a study schema in Section 1.2. The endpoints are defined in Section 3. There will be no outpatient digital monitoring during the optional cycles 3 and 4.

Number of Subjects

Participants in this clinical investigation shall be referred to as "subjects." Approximately 45 subjects will participate in this study. Refer to Section 9.2 for sample size considerations.

Summary of Subject Eligibility Criteria

Adult subjects with B-cell precursor (BCP) ALL with minimal/measurable residual disease (MRD) defined as a bone marrow (BM) blast count < 5%.

For a full list of eligibility criteria, please refer to Section 5.1 to Section 5.2.

Treatments

Investigational Product

Amgen Investigational Product Dosage and Administration: Blinatumomab is administered as a CiVI.

A single cycle of blinatumomab treatment is 6 weeks in duration, which includes 4 weeks of blinatumomab CiVI followed by a 2-week treatment-free interval. The treatment-free interval may be prolonged by up to 7 days, if deemed necessary by the investigator. For subjects \geq 45 kg, blinatumomab will be administered at a dose of 28 μ g/day for all 4 weeks of continuous treatment. Subjects < 45 kg will be administered blinatumomab 15 μ g/m²/day (max 28 μ g/day).

Date: 21 April 2022 Page 16 of 108

Non-investigational Product

Non-Amgen Non-investigational Product Dosage and Administration:

Dexamethasone

Premedication with dexamethasone (or prednisone): Dexamethasone 16 mg (or equivalent prednisone 100mg) intravenously (IV): up to 6 hours before start of treatment in each treatment cycle. Subjects ≥ 45 kg will have 2 additional 8 mg doses (subjects < 45 kg will receive 2 doses of 5 mg/m² rounded to the nearest mg) of oral dexamethasone to use as needed for treatment of CRS symptoms only if instructed by HCP. It will be recommended that hospitalization be strongly considered for subjects who require interruption of blinatumomab for > 4 hours.

Procedures

Written informed consent must be obtained from all subjects before any study-specific screening procedures are performed. Study-specific procedures will occur according to the Schedule of Assessments (Table 1-2)

For a full list of study procedures, including the timing of each procedure, please refer to Section 8.2 and the Schedule of Activities in Table 1-2.

Statistical Considerations Sample Size Considerations:

The planned enrollment for this study is **approximately** 45 patients. The sample size is based on feasibility rather than on statistical considerations. Given a true probability of a primary endpoint event of 38%, the expected 95% upper confidence limit with 45 subjects would be 53.5%. The 38% subject incidence rate is based **on** the SAE rate in first 3 days of cycle 1 and first 2 days of cycle 2 from the previous MRD study (BLAST). Based on these assumptions, we expect to observe approximately 17 subjects who will experience the primary endpoint which should provide an initial indication of the timeliness of the therapeutic intervention when outpatient blinatumomab in administered in conjunction with remote digital monitoring.

Planned Analyses:

Interim Analyses: Safety data will be reviewed on an ongoing basis. A data review team (DRT), internal to Amgen but external to the study team, will assess safety after every fifth non-replaceable subject has been dosed and given an opportunity to complete MDMP. Refer to Section 4.2.1 for details on replacement of subjects.

Date: 21 April 2022 Page 17 of 108

Primary analysis: The primary analysis will occur when all subjects end the study.

Final Analysis: The primary analysis will also be the final analysis.

Descriptive statistics for demographic and safety will be summarized as appropriate. For categorical variables, the number and percentage of subjects in each category will be summarized. Continuous variables will be summarized by n, mean, standard deviation, median, Q1 (25th percentile), Q3 (75th percentile), minimum, and maximum values.

For a full description of statistical analysis methods, please refer to Section 9.

Statistical Hypotheses

No formal statistical hypothesis will be tested.

[figure not shown]
Sponsor Name: Amgen

Page 18 of 108 Date: 21 April 2022

1.2 **Study Schema**

Figure 1-1. Study Schema

ALL = acute lymphoblatic leukemia; CIVI = Continuous IV infusion; CR = Complete Remission; MRD = Minimal/Measurable Residual Disease

aScreening must be completed within 21 days of enrollment. Eligibility CR and MRD bone marrow assessments must be no more than 14 days prior to informed consent. Screening to establish digital health monitoring baseline must be completed within 7 days of enrollment. Digital Health monitoring devices will be tested for a minimum of 24 hours.

^B End of Cycle 2 clinical assessment to be performed on day 29 pf cycle 2.

^c End of Study to be conducted 30 (+3 days) after last dose of blinatumomab

All MRD assessments per institutional standard of care procedures. No central MRD testing will be required Subjects can be transplanted at any time according to institutional guidelines and Standard of Care.

Date: 21 April 2022 Page 19 of 108

Table 1-1. Vital Signs and Clinical Monitoring

AMG 103 20190014 VS and Clinical Monitoring

Panel 1

Education

- HCP, Subjects & Caregivers (CG)
 will receive training in the use
 and functions of the Current
 Health (CH) monitoring
 device(s)(CHDs), including the
 temperature sensor, BP monitor,
 and tablet
- Subject will wear CHDs during screening to establish baseline VS, comfort, and eligibility.
- Subject and CG will be trained to recognize clinical changes/symptoms such as increased lethargy, change in mental status, seizure, jitteriness, fever, fast or difficult breathing and other signs and symptoms
- Subject and CG will be educated on the usual side effects of blinatumomab (IP) infusion.
- Subject and CG will be educated to contact HCP for any change or new finding
- HCPs will be trained on outpatient IP infusion and response algorithm

Panel 2

Monitoring

Electronic monitoring including

- Establishment of Subject baseline during screening
- Remote monitoring of vital signs (VS): Respiratory rate (RR), Pulse rate (PR), temperature(T), Blood Pressure(BP), Oxygen saturation(S).
- Monitoring: Continuous PR, T, and S. intermittent: RR(every 30 secs) and BP(every 3 hrs.)
- HCP may order more frequent VS as needed.
- VS algorithm for ALERT to changes in VS as outlined, which are persistent for ≥ 10 minutes, with the exception of BP, alert will occur within 1 minute of measurement:
 - Systolic BP ≤ 100 mmHg or ≥ 20% reduction from baseline (established in screening)
 - Temp ≥ 38.0°C(100.4°F) (Axillary fever scout ≥37.0°C) (99.4°F))
 - S ≤ 92%
 - $R \le 10 \text{ or } \ge 25$
 - PR \leq 60 or \geq 150
- Neurological algorithm for intervention
 - Any seizure
 - Aphasia (receptive or expressive)
 - Apraxia
 - Altered level of consciousness
 - Impairment of cognitive skills
 - Motor weakness
 - Any change of grade ≥ 3 self-care activities of daily living
 - Any change identified by Patient or caregiver

Panel 3

Intervention

- Subject proximity (≤ 1 hr.) to a advanced medical center
- Pre-dose dexamethasone(20mg) will be given prior to initiation of blinatumomab at every cycle.
- Oral dose(s) of steroid available at home, to be taken under HCP direction.
- On day 1 of cycle 1, subject to remain at infusion center for 5 hours after initiating blinatumomab.
 On day 1 of cycle 2, subject to remain at infusion center for 2 hours after initiating blinatumomab.
 - For cycles 3 and 4, HCP is to follow product information regarding patient monitoring
- Either
 - Abnormal VS (persistent for ≥ 10 minutes).
 - or change in clinical status by patient or CG report
- Will generate an immediate alert to HCP
- HCP will contact/communicate with Subject /CG via phone/tablet video monitoring
- HCP response per monitoring algorithm (panel 2)
- HCP will be able to contact Subject/CG for any concerns in absence of an alert
- Subject /CG will be able to contact HCP, or Emergency services directly as needed

BP = blood pressure; HCP = healthcare professional; IP = Investigational product

Date: 21 April 2022 Page 20 of 108

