9.4.2.3 Safety Analyses

9.4.2.3.1 Analyses of Primary Safety Endpoint(s)

Endpoint	Statistical Analysis Methods
Primary	Subject incidence rate of primary endpoint (grade 3 or 4 CRS, NT or any adverse event resulting in hospitalization during MDMP) will be summarized and accompanied by 2-sided 95% exact binomial confidence intervals (Clopper and Pearson, 1934).
Key Secondary	Time from first onset of the key secondary endpoint event to therapeutic intervention will be summarized as continuous variable with count of non-missing, mean, median, standard deviation, minimum and maximum for those experiencing the endpoint. Type of therapeutic intervention will be tabulated with n (see Section 9.4.2.4). If there are events that prevent the occurrence of therapeutic intervention, censoring based approach such as Kaplan-Meier may be used.
Secondary	The statistical analysis methods for adverse event and other safety endpoints are described in Section 9.4.2.3.2 through Section 9.4.2.3.4.
Exploratory	Not applicable

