For the purpose of this study, the mandatory device monitoring period (MDMP) is defined as the first three days of cycle 1 (72 hours) and the first 2 days of cycle 2 (48 hours) of blinatumomab infusion.

Therapeutic Intervention (TI)

Therapeutic intervention is any measurable action taken by the subject or performed on the subject as a result of the onset of the clinical parameters described. Such actions may include:

- Advised subject to go to hospital/ER immediately
- Advised subject to call 911 immediately
- Advised to suspend blinatumomab
- Advised to take antipyretic (e.g. acetaminophen)
- Advised subject to take dexamethasone
- Advised to suspend blinatumomab and take antipyretic
- Advised to suspend blinatumomab and take dexamethasone
- Advised to take other medication

• Other (if Other, describe the intervention)

Time to Therapeutic Intervention (TTI)

Time to therapeutic intervention is the time between the delivery of the device alert or unscheduled contact with HCP by subject/CG to report a change to the time of initiation of the therapeutic intervention.

TTI will be calculated as duration (in minutes) from time of the device alert (alarm triggered) to the time of initiation of the therapeutic intervention (i.e. when HCP silenced the alarm and advised an intervention).

If there is a case where the alarm is triggered, and the HCP advised an intervention, but event is not resolved and subject/CG presses the alarm again then that would be considered as a separate event (as alarm ID will be different) to calculate TTI.

TTI will be calculated for all the valid alarm triggers which leads to an intervention. If the calculated TTI is considered incongruous (i.e. more than 15min.) then a query will be entered in DIIR log.

All the scenarios defined below will be considered as invalid for calculation of TTI:

- If no intervention is required (e.g. technical issues) corresponding to an alarm.
- If intervention time is prior to the time of device alert (alarm triggered).

Treatment-emergent Adverse Event

Treatment-emergent Adverse Event is defined as adverse events starting on or after first dose of blinatumomab as determined by "Did event start before first dose of investigational product" equal to "No" or missing on the Events eCRF and up to the end of study visit.

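### The key secondary endpoint is titled as time from first onset, but TTI is computed from the alert or unscheduled contact, so detection delay is left out and the title does not describe the reported quantity

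*Protocol*

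**What the plan says.** The current documents give three different starts for the same clock.

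- **Onset.** The endpoint in the protocol synopsis and Section 3, repeated in SAP 2.1, is "Time (in minutes) from first onset of fever, hypotension, hypoxia, other grade 3 or 4 vital sign including seizure or neurological change" to therapeutic intervention. The analysis table in protocol 9.4.2.3.1 agrees: "Time from first onset of the key secondary endpoint event to therapeutic intervention will be summarized as continuous variable".
- **Detection.** The objective paired with that endpoint is "To determine the time from first detection of grade 3 or 4 vital sign, or significant clinical change to therapeutic intervention". Detection is not defined.
- **Alert or contact.** Footnote a, attached to the endpoint, says that TTI "is the measured time between the delivery of the device alert or unscheduled contact with HCP by subject/CG to report a change", ending when the intervention begins. SAP Section 5 repeats this and adds: "TTI will be calculated as duration (in minutes) from time of the device alert (alarm triggered) to the time of initiation of the therapeutic intervention". SAP 9.6.1 then summarises TTI as defined there.

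Two features of the monitoring separate these starts. The synopsis says that an alert is generated "once the preset threshold values are surpassed and sustained for at least 10 minutes". Blood pressure is not monitored continuously: the subject takes it every 3 hours, and the HCP may extend the interval to at most 6 hours after the first 24 hours.

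SAP Section 10 lists rewording of the primary endpoint and of other secondary endpoints. It lists no change to this one.

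**The concern.** Onset, detection and alert are different moments. By construction the alert comes last for any sign subject to the persistence rule, and a low blood pressure can be found only at the next reading. Nothing in the plan adds the earlier time back. A computed TTI therefore cannot be the quantity named in the endpoint title.

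This matters because the sample-size sections (protocol 9.2, SAP 3.2) justify the study partly by the early indication it should give of how timely intervention is under remote monitoring. If the title stands, a result table could present the response delay as the whole delay from onset. The point concerns only where the clock starts, not where it stops.

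**Working it through.** **The plan's own figure.** The documents give no target, expected value or precision for TTI. The only numerical design figure is the 53.5% expected upper 95% limit for the primary endpoint at a 38% rate with 45 subjects. It reproduces: the expected count is 45 × 0.38 = 17.1; the Clopper-Pearson upper limit for 17/45 is 53.46%; the upper limit averaged over Binomial(45, 0.38) is 53.52%. It says nothing about TTI.

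**Inputs for the clock.**
- Persistence hold: at least 10 minutes (synopsis; Table 1-1; Appendix 8).
- Alert step after receipt: within 1 minute, with BP treated separately (synopsis).
- BP interval: 3 h = 180 min, extendable to 6 h = 360 min after the first 24 hours (synopsis; Table 1-2).
- Illustrative TTI: 15 min. SAP Section 5 queries TTI values above this limit. It is not an expected value.

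**Formula.** Onset to intervention = pre-alert interval + TTI.

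| Event type | Omitted interval against the onset title | Onset to intervention if TTI = 15 min |
|---|---|---|
| Temperature, SpO2, low pulse, low respiratory rate | at least 10 min; 10 to 11 min with the alert step if the alert follows at once | 15 + 10 = 25 to 15 + 11 = 26 min |
| Pulse ≥150, respiratory rate ≥25 | as above, or no hold omitted if the 10 min is part of the event | 25 to 26 min, or 15 to 16 min |
| Hypotension, 3-hour readings | 0 to 180 min, unknown | at most 15 + 180 = 195 min |
| Hypotension, 6-hour readings | 0 to 360 min, unknown | at most 15 + 360 = 375 min |
| Subject or caregiver contact | symptom onset to contact, not bounded by the documents | cannot be stated |

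The second row reflects Appendix 8, which calls a high pulse or high respiratory rate severe when it has lasted 10 minutes. Its definitions of fever, hypoxia and hypotension contain no duration, and it has no entry for low pulse or low respiratory rate.

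If hypotension began at a uniformly random time between readings and lasted to the next one, the mean omitted interval would be 180/2 = 90 min or 360/2 = 180 min. That is an assumption, not something the documents give.

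The hold and the BP interval concern different signs and are not summed. The synopsis and Table 1-1 also word the BP exception differently, so no 10-minute hold is applied to BP here.

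**Against the objective.** Time between BP readings precedes detection, so none of the 180 or 360 minutes is missing from a time that starts at detection. For continuously monitored signs the answer depends on the undefined term: if detection means the first out-of-range reading, the hold is still missing; if it means the alert, nothing is.

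**The case against.** The strongest reply is that the working definition is disclosed. Footnote a hangs on the endpoint itself, SAP Section 5 repeats it, and SAP 9.6.1 names the summarised quantity as TTI. A reader might infer a concealed or faulty calculation; the documents do not support that. Alert-to-intervention time is a legitimate measure, and the defect lies in the title. The disclosure does not remove the conflict, however, because protocol 9.4.2.3.1 and SAP 2.1 still say onset.

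On size, most of the reply stands.
- A reader might infer that every device alarm understates the delay by at least 10 minutes. Appendix 8 prevents that for high pulse and high respiratory rate.
- A reader might take 180 or 360 minutes as the bias for hypotension. They are maxima. The HCP may order more frequent readings, a caregiver is present throughout and can raise an alarm, and the first 5 hours of cycle 1 are spent at the infusion center.
- A reader might want the figure set against inpatient care. The study has no comparator and no hypothesis, and plans no such comparison.

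It is also fair that recovering the pre-alert time may not be simple. Table 1-2 puts only 3-hourly medians in the eCRF, and SAP 8.2 does not state the resolution of the device data transferred.

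**Conclusion.** The point holds as a conflict between the endpoint's title and its calculation, present in the current protocol and carried into the SAP. Followed as written, the plan reports time from alert or contact to intervention under a title that promises time from onset.

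Against that title the omission is at least 10 minutes for temperature, SpO2, low pulse and low respiratory rate. It is arguable for high pulse and high respiratory rate. For hypotension it is unknown, up to 180 or 360 minutes, and for contact-initiated events it is unmeasured. The 10 minutes follows from the alert rule; the BP figures assume only that readings follow the stated schedule.

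The stronger reading, that TTI is too short by a fixed amount for all events, is not supported. The shortfall depends on the sign and on which of the three starting points is meant, and the BP interval is no shortfall against the objective. What should change before database lock is the wording, because it determines what the trial can claim about timeliness.

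**What to change.** Rename the endpoint *time from device alert or unscheduled contact to therapeutic intervention* in the protocol synopsis, Section 3, protocol 9.4.2.3.1 and SAP 2.1. Align the objective's use of detection with it, record the change in SAP Section 10, and state that detection delay is not included. This needs no new data.

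Then confirm whether the transferred device data contain time-stamped readings. If they do, add to SAP 9.6.1 a supplementary summary of (a) first out-of-range reading to alert and (b) first out-of-range reading to intervention. For BP, give the time since the last in-range reading as the upper bound on detection delay. If they do not, the renaming and the explicit statement are enough.

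The cost is wording in four places, one entry in SAP Section 10 and, where the data allow, a small extra derivation. The stated delay will look less favourable. No alert threshold, measurement schedule or clinical rule changes.
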